## 1.2 BACKGROUND ON RANIBIZUMAB

Ranibizumab is a recombinant humanized IgG1  $\kappa$  isotype monoclonal antibody fragment administered by intravitreal administration. It binds to and inhibits the biologic activity of VEGF-A. Ranibizumab is produced by standard recombinant technology methods in an *Escherichia coli* expression vector and bacterial fermentation. Ranibizumab is not glycosylated and has a molecular mass of approximately 48,000 daltons.

Current U.S. prescribing information supports monthly intravitreal injection of ranibizumab 0.5 mg for treatment of nAMD and also provides information on results that may be expected following less frequent than monthly dosing after an initial loading phase.

Refer to the PDS Investigator's Brochure for details about nonclinical and clinical ranibizumab studies.

### 1.3 BACKGROUND ON THE PORT DELIVERY SYSTEM WITH RANIBIZUMAB

The PDS is a drug delivery technology that allows physicians to use ranibizumab with a continuous drug delivery profile without altering its chemistry and consists of an intraocular implant (hereafter referred to as the implant), four ancillary devices (insertion tool, initial fill needle, refill needle, and explant tool), and a customized formulation of ranibizumab tailored for continuous delivery (see Appendix 16).

The implant is an intraocular refillable device that is surgically implanted through the pars plana to allow for a continuous delivery of ranibizumab into the vitreous. After insertion of the implant, the proximal end of the implant (flange) sits on top of the sclera, under the conjunctiva and Tenon's capsule, with the body of the implant extending into the vitreous. The implant is used in conjunction with the customized formulation of ranibizumab to precisely control the rate and duration of drug delivery and is refillable through the implant septum in situ.

For additional PDS details (e.g., fill, insertion, refill-exchange, and explantation of the implant), consult the PDS instructions for use (IFU) document and the PDS Investigator's Brochure.

Prior to this current study, the implant has been investigated in prospective Phase I and II studies. A prospective Phase I, open-label study in patients with nAMD was conducted by the device developer, ForSight VISION4, Inc. (FSV4), at a single site in Latvia. The study investigated the safety, tolerability, and duration of ranibizumab exposure delivered with the implant. The implant used in Phase I was composed of biocompatible materials (polymethyl methacrylate, silicone, and 316L stainless steel; see Appendix 16).

For additional details about the Phase I study, see Section 1.4 and the PDS Investigator's Brochure. The implant evaluated in Phase II was composed of biocompatible materials (polysulfone, silicone, and titanium; see Appendix 16).

## 1.3.1 Phase I Port Delivery System with Ranibizumab Study: FH-1.2

The safety, tolerability, and duration of ranibizumab (10 mg/mL) exposure delivered through the implant were investigated in a Phase I prospective, open-label study (FH-1.2) in a patient population with nAMD and conducted by FSV4 at a single site in Latvia. Patient enrollment was initiated in August 2010, and the study assessed the safety of the PDS in 20 eyes through the collection and analysis of adverse events and complications, including procedure-related adverse events, device-related adverse events, ranibizumab-related adverse events, and all general health and patient-reported adverse events.

All 20 patients completed the planned 12-month treatment phase of the Phase I study. No patients were treated via the implant after the first 12 months of the study. At

**Port Delivery System with Ranibizumab—F. Hoffmann-La Roche Ltd.** 28/Protocol GR40548, Version 5

Month 12, 6 patients underwent per-protocol planned implant removal and discontinued from the study after completion of the Month 13 visit. Of the 14 remaining patients eligible for an additional 24-month safety-monitoring phase (quarterly safety visits), 1 patient was lost to follow-up after 12 months. The remaining 13 patients continued in the safety-monitoring phase; and 1 of the 13 patients was subsequently lost to follow-up after 21 months. Follow-up data out to 36 months are available for the remaining 12 patients.

A total of 95 adverse events were reported in all 20 patients (100%) in this study: 87 adverse events during the 12-month treatment phase and 8 adverse events during the safety-monitoring phase. Of the 87 adverse events reported during treatment, 76 events were considered by the investigator to be related (possibly, probably, or definitely) to the implant insertion procedure, the refill-exchange procedure, the implant removal procedure, or study drug treatment.

The most common study-related adverse events were conjunctival hyperemia (59%), vitreous hemorrhage (7%), hyphema (7%), VA decrease (5%), eye dryness (4%), and conjunctival edema (3%). Conjunctival hyperemia occurred in 19 of 20 patients (95%), for a total of 45 events; 44 of those events (98%) were mild in severity and 1 event was of moderate severity. Conjunctival hyperemia was typically observed following the implant insertion or refill-exchange procedures, and the average duration of these events was 8 days, with all resolving over a range from 3 to 48 days from onset.

A total of 96 implant refill-exchange procedures were performed in the study. The most frequently reported adverse events considered by the investigator to be related to the implant refill-exchange on a per-procedure basis were conjunctival hyperemia (33%), eye dryness (2%), vitreous haze (2%), increased lacrimation (1%), and ocular discomfort (1%). The adverse event rate per implant refill-exchange procedure was 38%. The adverse events were of mild severity, and the average duration to resolution was 7 days.

Refer to the PDS Investigator's Brochure for further details.

### 1.3.2 Phase II Port Delivery System with Ranibizumab: Study GX28228 (Ladder)

Subsequent to Study FH-1.2, a Phase II, dose-ranging, randomized, active treatment–controlled, multicenter study (GX28228 [Ladder]) was initiated to evaluate the safety, efficacy, and pharmacokinetics of three different doses of ranibizumab (10 mg/mL, 40 mg/mL, and 100 mg/mL) delivered via the PDS versus monthly intravitreal ranibizumab 0.5 mg injections in patients with nAMD and a history of positive response to any anti-VEGF therapy. The study, which was U.S. based, was approximately 43 months in duration. The last patient, last visit occurred on 28 March 2019 and the final study analysis was then conducted (snapshot date of 2 May 2019).

The primary analysis, performed when all enrolled patients had been followed up for 9 months, measured the time at which a patient first required an implant refill-exchange according to protocol-defined refill-exchange criteria. In the PDS 100 mg/mL, PDS 40 mg/mL, and PDS 10 mg/mL arms, the median time to first refill-exchange was 15.0, 13.0, and 8.7 months, respectively. In addition, 79.8%, 71.3%, and 63.5% of patients went  $\geq$ 6 months without requiring a refill-exchange in PDS 100 mg/mL, PDS 40 mg/mL, and PDS 10 mg/mL, respectively. *Best-corrected visual acuity* (BCVA) and anatomic outcomes were comparable between the PDS 100 mg/mL arm and the monthly intravitreal ranibizumab 0.5 mg arm. The overall safety profile from the primary analysis revealed a favorable benefit–risk assessment. The optimized implant insertion surgery and refill-exchange procedures were generally well tolerated. Systemic safety profile of PDS treatment was well characterized and comparable with monthly intravitreal ranibizumab 0.5 mg treatment (Campochiaro et al. 2019). Results from the final analysis were consistent with the results from the primary analysis (*Khanani et al. 2020*). *R*efer to the PDS Investigator's Brochure for further details.

Patients from Study GX28228 who completed the study and consented to the open-label extension study (GR40549 [Portal]) have now enrolled.

## 1.4 STUDY RATIONALE AND BENEFIT-RISK ASSESSMENT

As a result of the chronic, progressive nature of nAMD, frequent intravitreal ranibizumab 0.5 mg injections continue for extended periods for many patients. The pivotal Phase III Studies MARINA (FVF2598g) and ANCHOR (FVF2587g) in nAMD demonstrated significant and well-maintained VA outcomes with monthly intravitreal ranibizumab 0.5 mg injections for 2 years.

The Study HARBOR (FVF4579g), which compared monthly with *as needed* (PRN) ranibizumab administration, showed comparable efficacy and maintenance of visual and anatomic improvements for 2 years between the two regimens. However, all patients were evaluated monthly to determine the need for retreatment and still required frequent injections. The mean number of intravitreal ranibizumab 0.5 mg injections through Month 24 was 21.4 injections for the monthly treatment arm and 13.3 injections for the PRN treatment arm. In clinical practice, frequent office monitoring visits are required and regular injections are necessary to maintain optimal vision gains; however, this places a significant burden on patients and their caregivers, treating physicians, and the healthcare system.

Such requirements present a substantial barrier to maintenance of desired efficacy outcomes. Indeed, in clinical practice, many patients are treated less frequently than per the approved prescribing information and as a consequence experience suboptimal efficacy (Holz et al. 2015; Maguire et al. 2016; Egan et al. 2017; Rao et al. 2018). As such, there remains a substantial unmet need for an optimized treatment and dosing regimen that could alleviate the current treatment burden on patients, caregivers, and healthcare providers and consequently improve vision outcomes in clinical practice.

**Port Delivery System with Ranibizumab—F. Hoffmann-La Roche Ltd.** 30/Protocol GR40548, Version 5

Continuous delivery of ranibizumab from the implant, with a prolonged fixed period between refill-exchanges, is a novel approach that may result in less-frequent need for retreatment than monthly dosing and patient monitoring. The decrease in treatment burden may reduce the risk of intravitreal injection–related adverse events, increase compliance, and reduce the burden to patients, their caregivers, and the healthcare system, while maintaining optimal visual outcomes.

The primary analysis of the results of the Phase II GX28228 (Ladder) study revealed a favorable benefit–risk assessment for the PDS, which was well tolerated, with no evidence of dose dependency on the frequency or severity of the reported adverse events. The overall safety profile of the PDS from available study data is generally consistent with the known safety profile of both ranibizumab administered by intravitreal injection (Lucentis® U.S. Package Insert [USPI]) and similar surgical procedures involving intraocular implants (Dunn et al. 2004; Gedde et al. 2012; Buys 2013; Retisert® U.S. Package Insert; Vitrasert® Implant U.S. Package Insert). See Section 5.1.3 for anticipated risks associated with the PDS or implant insertion procedure. For a complete summary of safety information, refer to the PDS Investigator's Brochure.

The Phase I and II studies provide evidence of the safety and tolerability of the PDS and support the evaluation of the PDS in a Phase III study.

## 2. OBJECTIVES AND ENDPOINTS

This study will evaluate the efficacy, safety, and pharmacokinetics of ranibizumab delivered via the PDS implant compared with ranibizumab 0.5 mg delivered as a monthly intravitreal injection in patients with nAMD. Specific objectives and corresponding endpoints for the study are outlined in Table 1.

### Table 1 Objectives and Corresponding Endpoints

Primary Efficacy Objective	Corresponding Endpoint
• To evaluate the non-inferiority and equivalence in efficacy of ranibizumab delivered via the PDS Q24W with the 100-mg/mL formulation compared with that of 10-mg/mL (0.5-mg dose) Q4W intravitreal ranibizumab injections	
 
Change from baseline in BCVA score at the average of Week 36 and Week 40, as assessed using the ETDRS visual acuity chart at a starting distance of 4 meters
 

Secondary Efficacy Objectives	Corresponding Endpoints
To evaluate the relative efficacy of ranibizumab delivered via the PDS Q24W with the 100-mg/mL formulation compared with that of 10-mg/mL (0.5- mg dose) Q4W intravitreal ranibizumab injections, as assessed by visual acuity	
 
Change from baseline in BCVA score averaged over Week 60 and Week 64
 

	
 
Change from baseline in BCVA score over time
 

	
 
Proportion of patients with BCVA score of 38 letters (20/200 approximate Snellen equivalent) or worse at the average over Week 36 and Week 40
 

	
 
Proportion of patients with BCVA score of 38 letters (20/200 approximate Snellen equivalent) or worse over time
 

	
 
Proportion of patients with BCVA score of 69 letters (20/40 approximate Snellen equivalent) or better at the average over Week 36 and Week 40
 

	
 
Proportion of patients with BCVA score of 69 letters (20/40 approximate Snellen equivalent) or better over time
 

	
 
Proportion of patients who lose < 10 or < 5 letters in BCVA score from baseline to the average over Week 36 and Week 40
 

	
 
Proportion of patients who lose < 10 or < 5 letters in BCVA score from baseline over time
 

	
 
Proportion of patients who gain ≥0 letters in BCVA score from baseline to the average over Week 36 and Week 40
 

	
 
Proportion of patients who gain ≥0 letters in BCVA score from baseline over time
 

 
To evaluate the relative efficacy of ranibizumab delivered via the PDS Q24W with the 100-mg/mL formulation compared with that of 10-mg/mL (0.5-mg dose) Q4W intravitreal ranibizumab injections, as assessed by CPT on SD-OCT
 
	
 
Change from baseline in CPT at Week 36
 
Change from baseline in CPT over time
 

• To evaluate the proportion of patients who undergo supplemental treatment with intravitreal ranibizumab 0.5 mg	• Proportion of patients in the implant arm who undergo supplemental treatment with intravitreal ranibizumab 0.5 mg before the first, second, third, and fourth fixed refill-exchange intervals
	• Proportion of patients in the implant arm that undergo a supplemental treatment that requires subsequent additional supplemental treatments during the study

Exploratory Efficacy Objectives	Corresponding Endpoints
• To evaluate the impact of supplemental treatment with intravitreal ranibizumab 0.5 mg	
 
Endpoints will be results-dependent based on number of supplemental treatments
 

 
To evaluate the relative efficacy of ranibizumab delivered via the PDS Q24W with the 100-mg/mL formulation compared with that of 10-mg/mL (0.5- mg dose) Q4W intravitreal ranibizumab injections, as assessed by central subfield thickness on SD-OCT
 
	
 
Change from baseline in CST at Week 36
 
Change from baseline in CST over time
 

 
To assess clinically relevant features using advanced analytics tools (including artificial intelligence-based tools) on multimodal images and clinical data
 
	Clinically relevant features over time

 
To evaluate the development of macular atrophy in patients treated with the PDS Q24W with the 100- mg/mL formulation compared with those with 10-mg/mL (0.5-mg dose) Q4W intravitreal ranibizumab injections.
 
	
 
Proportion of patients with macular atrophy at baseline, Weeks 36, 48, and 96
 
Change from baseline in macular atrophy area at Weeks 36, 48 and 96
 

 
To evaluate the relative efficacy of ranibizumab delivered via the PDS Q24W with the 100-mg/mL formulation compared with that of 10-mg/mL (0.5- mg dose) Q4W intravitreal ranibizumab injections, as assessed by visual acuity
 
	
 
Proportion of patients who gain ≥5 letters in BCVA score from baseline over time.
 

Safety Objective	Corresponding Endpoints
• To evaluate the safety and tolerability of ranibizumab, delivered via the PDS Q24W with the 100-mg/mL formulation compared with that of 10- mg/mL (0.5-mg dose) Q4W intravitreal ranibizumab injections	
 
Incidence and severity of ocular and systemic (non-ocular) AEs
 
Incidence, severity, and duration of AESIs
 
Incidence, severity, and duration of ocular AESIs during the postoperative period (up to 37 days of initial implantation) and follow-up period (>37 days after implantation surgery)
 

Pharmacokinetic Objective	Corresponding Endpoints
• To characterize the serum pharmacokinetics of ranibizumab in patients after the initial fill and subsequent refill-exchanges in patients with the PDS	
 
Observed serum ranibizumab concentrations at specified timepoints
 
Additional estimated PK parameter values, including AUC0-6M, Cmax, Cmin, and t1/2 after PDS implant insertion
 

Exploratory Pharmacokinetic Objectives	Corresponding Endpoints
• To evaluate potential relationships between drug exposure and the efficacy of the PDS	
 
Relationship between serum concentration or PK parameters for ranibizumab delivered via the PDS and efficacy endpoints
 

To characterize ranibizumab aqueous     humor concentration over time	
 
Observed aqueous humor ranibizumab concentrations over time
 

Immunogenicity Objective	Corresponding Endpoint
• To investigate the formation of serum anti-ranibizumab antibodies	The incidence of ADAs during the study, grouped in the following manner:
	
 
Patients who were ADA negative at baseline and became positive only after dosing
 

	
 
Patients who were ADA positive at randomization and ADA titer increased after dosing
 

	
 
Patients who were ADA positive at randomization and ADA titer did not increase after dosing
 

Exploratory Biomarker Objectives	Corresponding Endpoints
• To explore relationships between aqueous humor free-VEGF concentrations over time and the efficacy of ranibizumab, delivered via the PDS Q24W with the 100-mg/mL formulation	
 
Comparison of patients with and without aqueous humor free-VEGF present between refill-exchanges and needing supplemental treatment
 
Comparison of patients with and without aqueous humor free-VEGF present between refill-exchanges and CST changes from bacaging over time
 

	
 
Comparison of patients with and without aqueous humor free-VEGF present between refill-exchanges and BCVA score change from baseline over time
 

To identify biomarkers that are prognostic of response to ranibizumab, are associated with acquired resistance to ranibizumab, are associated with susceptibility to developing adverse events (i.e., safety biomarkers), can provide evidence of ranibizumab activity (i.e., pharmacodynamic biomarkers), or can increase the knowledge and understanding of AMD-related diagage biology.	
 
Relationship between biomarkers in blood and aqueous humor with disease characteristics and response to ranibizumab
 
Relationship between genetic variants (such as AMD risk alleles, polymorphisms within the complement pathway, and polymorphisms within the VEGF-A genetic locus) with the disease characteristics and/or response to treatment with ranibizumab
 
Relationship between imaging features with disease characteristics and/or response to treatment with ranibizumab
 

Exploratory Patient Experience Objectives	Corresponding Endpoints

 
To evaluate the preference of patients for ranibizumab delivered via the PDS for 40 weeks compared to intravitreal anti-VEGF treatment received in the 6 months prior to Day 1
 
	• Proportion of patients who report preferring ranibizumab treatment via the PDS compared with intravitreal anti-VEGF treatment, as assessed by the PPPQ, at Week 40 among patients in the implant arm
• To evaluate patient-reported treatment satisfaction with ranibizumab delivered via the PDS for 40 weeks compared with that of Q4W intravitreal ranibizumab injections, as assessed by the MacTSQ	
 
MacTSQ total score at Week 40
 

ADA= anti-drug antibody; AE = adverse event; AESI = adverse event of special interest; AMD = age-related macular degeneration; AUC0-6M = area under the concentration-time curve from 0 to 6 months; BCVA = best-corrected visual acuity;  $C_{max}$  = maximum serum concentration;  $C_{min}$  = minimum serum concentration; CPT = center point thickness; CST = central subfield thickness; ETDRS = Early Treatment Diabetic Retinopathy Study; MacTSQ = Macular Degeneration Treatment Satisfaction Questionnaire; PDS = Port Delivery System with ranibizumab; PK = pharmacokinetic; PPPQ = PDS Patient Preference Questionnaire; Q4W = every 4 weeks; Q24W = every 24 weeks; SD-OCT = spectral domain optical coherence tomography;  $t_{1/2}$  = half-life; VEGF = vascular endothelial growth factor.

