#### Study Eye

- Subretinal hemorrhage that involves the center of the fovea, if the hemorrhage is greater than 0.5-disc area (1.27 mm^2) in size at screening
- Subfoveal fibrosis or subfoveal atrophy

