#### 6.4.3 Exploratory Endpoints

Details regarding the exploratory endpoints will be provided in the SAP.

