#### 4.4 EFFICACY ANALYSIS

The efficacy analyses will be based on the Efficacy Population.

Patients in the PDS 100 mg/mL arm can receive intravitreal ranibizumab injection as supplemental treatment if they meet the criteria described in Section 2.

Unless otherwise noted, analyses of efficacy outcome measures will be stratified by baseline BCVA (<74 letters vs.≥74 letters). The stratification factor as recorded in IxRS will be used. The estimates and confidence intervals (CIs) will be provided for the mean (for continuous variables) or proportion (for binary variables) for each treatment group and the difference in means or proportions between two treatment groups. All CIs will be two-sided and at the 95.03% level (see Section 3.3).

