  - Receives any prohibited systemic treatment or prohibited therapy in the Study eye (Section 4.4.2 of the Protocol)
  - Discontinuation study treatment due to AEs
  - Discontinuation study treatment due to lack of efficacy as per investigator's clinical judgment.
- Population-level summary: Difference in proportions between PDS 100 mg/ml and intravitreal groups

The proportion of patients in each treatment group and the overall difference in proportions between treatment groups will be estimated using the weighted average of the observed proportions and the differences in observed proportions over the strata defined by randomization stratification factor of baseline BCVA (< 74 letters vs. ≥ 74 letters) using the Cochran-Mantel-Haenszel (CMH) weights (Cochran 1954; Mantel and Haenszel 1959). All observed measurements will be included in the analysis regardless whether or not a patient has an intercurrent event. Confidence intervals of the proportion of patients in each treatment group and the overall difference in proportions between treatment groups will be calculated using the normal approximation to the weighted proportions (Mehrotra and Railkar 2000). If the response rate is low, an unstratified analysis may also be performed.

In addition, the binary secondary endpoints through Week 40 will also be summarized using the same approach with missing assessments imputed with the last post-baseline observation carried forward (continuous BCVA values are carried forward and then the binary endpoint is derived).

Different strata will be used for the CMH analyses of the following binary endpoint:

Proportion of subjects with a BCVA score of 69 letters (approximate 20/40 Snellen equivalent) or better at the average over Weeks 36 and 40: the difference between the two treatment groups will be estimated using the same approach stratified by baseline BCVA (Snellen equivalent of 20/40 or better vs. worse than 20/40).

The continuous secondary endpoints will be summarized using descriptive statistics based on all observed data. These continuous endpoints will also be analyzed following

the same method as the analysis of the primary endpoint (see Section 4.4.1) with the independent variable, baseline BCVA score (continuous), in the model replaced with the baseline value of the corresponding endpoint (e.g., baseline CPT). The intercurrent events and data handling rules for the primary endpoint will apply here.

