# 4.4.3 Exploratory Efficacy Endpoints

Exploratory endpoints are:

- BCVA and CST results over time relative to supplemental treatment
- Change from baseline in CST at Week 36
- Change from baseline in CST over time
- Proportion of patients with macular atrophy at baseline, Weeks 36, 48, and 96
- Change from baseline in macular atrophy area at Weeks 36, 48 and 96
- Proportion of patients who gain ≥5 letters in BCVA score from baseline over time.
- Proportion of patients who lose < 15 letters in BCVA score from baseline to the average over Week 88 and Week 92

 Proportion of patients who gain > 15 letters in BCVA score from baseline to the average over Week 88 and Week 92

To evaluate the impact of supplemental treatment with intravitreal ranibizumab on efficacy endpoints for the PDS 100 mg/ml group patients receiving supplemental treatment, graphs by patient showing BCVA and CST over time and indicating times of refill-exchange or supplemental treatments will be provided.

Change from baseline in CST at Week 36 and over time will be analyzed using the same analysis method and data handling rules as the primary endpoint.

Proportion of patients with macular atrophy and macular atrophy area will be analyzed by descriptive summaries including confidence intervals at each timepoint.

The other binary endpoints will be analyzed using the same method as the binary secondary endpoints (see Section 4.4.2).

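### The SAP compares change in macular atrophy area without adjusting for baseline area; an adjusted estimate would be an optional, low-cost addition

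*Protocol*

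**What the plan says.** Protocol Table 1 lists "Change from baseline in macular atrophy area at Weeks 36, 48 and 96" among the exploratory efficacy endpoints. The objective it serves is to evaluate the development of macular atrophy under the implant against monthly intravitreal ranibizumab. The protocol sets no method; section 6.4.3 says "Details regarding the exploratory endpoints will be provided in the SAP".

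SAP 4.4.3 then states: "Proportion of patients with macular atrophy and macular atrophy area will be analyzed by descriptive summaries including confidence intervals at each timepoint". No model and no covariate is named. The general rules in SAP 4.4 still apply: "analyses of efficacy outcome measures will be stratified by baseline BCVA" (below 74 letters against 74 or more), and estimates with 95.03% CIs are to be given for each group and for "the difference in means or proportions between two treatment groups". So an arm contrast with an interval is planned, but lesion size plays no part in it beyond the subtraction in the change score.

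Other continuous endpoints are handled differently. In SAP 4.4.2, continuous secondary endpoints use the primary model with baseline BCVA replaced by the "baseline value of the corresponding endpoint (e.g., baseline CPT"). In SAP 4.4.3 itself, CST is tied to the analysis of the primary endpoint: the sentence runs "Change from baseline in CST at Week 36 and over time will be analyzed using the same analysis method and data handling rules as the" and closes by naming that endpoint.

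On baseline data, Protocol 3.1 has the reading center assess screening images for lesion details that include macular atrophy. The schedules of activities place fundus photography, angiography and autofluorescence at screening and at Weeks 36, 48 and 96. Protocol 4.1.2.2 excludes "Subfoveal fibrosis or subfoveal atrophy" in the study eye, so eyes with atrophy elsewhere in the macula can enter.

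**The concern.** The objective is comparative, and a change from baseline cannot be computed without a baseline area, so the covariate is already in hand. Among the continuous change-from-baseline efficacy endpoints, atrophy area is the one that gets no model, and the SAP gives no reason.

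Area change may well depend on starting area. A circular lesion of radius R whose border advances by a grows by 2πRa + πa², so equal border advance adds more area to a larger lesion. If change and baseline are correlated, two things follow. The unadjusted interval is wider than the data require. And if one arm happens to receive more of the larger lesions, the observed difference moves for that reason alone. At stake is how well an exploratory comparison can be read, not any confirmatory claim.

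**Working it through.** **Plan's own figures.** The documents give no SD, correlation, prevalence or power for atrophy area, so there is nothing on this endpoint to reproduce. The stated power concerns BCVA only. The interval level does follow from SAP 3.3: 0.05 − 3 × 0.0001 = 0.0497, hence 95.03%.

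**Inputs.** 418 enrolled (Protocol 6.1) at 3:2 gives about 251 and 167. Let r be the within-arm correlation of area change with baseline area. It is not in the documents, so a range is shown.

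**Step 1, precision.** The unadjusted SE is SD(change) × √(1/n₁ + 1/n₂). Adjusting for baseline area multiplies it by √(1 − r²). The same gain without adjustment would need 1/(1 − r²) − 1 more patients.

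| r (assumed) | SE ratio | CI shorter by | Equivalent extra patients |
|---|---|---|---|
| 0 | 1.000 | 0% | 0% |
| 0.1 | 0.995 | 0.5% | 1% |
| 0.3 | 0.954 | 4.6% | 10% |
| 0.5 | 0.866 | 13.4% | 33% |
| 0.6 | 0.800 | 20% | 56% |

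**Step 2, chance imbalance.** The difference in mean baseline area has SD √(1/251 + 1/167) = 0.10 baseline SDs, with a 95% limit of 1.96 × 0.0998 = 0.20. An imbalance at that limit shifts the unadjusted difference by r × 0.196 SDs of change: 0.02, 0.06 or 0.10 for r = 0.1, 0.3 or 0.5.

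**Step 3, what that does to the interval.** With no true effect, and given an imbalance of k standard errors, the standardized difference is normal with mean rk and variance 1 − r². The 95.03% CI excludes zero when its absolute value exceeds 1.963.

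| r (assumed) | k = 0 | k = 1.96 |
|---|---|---|
| 0.1 | 4.9% | 5.3% |
| 0.3 | 4.0% | 7.9% |
| 0.5 | 2.3% | 12.9% |

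Averaged over all randomizations the figure is 4.97% for every r. The rate falls below nominal when the arms are balanced and rises above it when they are not.

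**Step 4, why r may exceed zero, and by visit.** This is an illustration on an assumed circular lesion, not a document figure. With a = 0.3 mm, a 0.5 mm² lesion (R = 0.399 mm) gains 0.75 + 0.28 = 1.03 mm², and a 6 mm² lesion (R = 1.382 mm) gains 2.60 + 0.28 = 2.89 mm². The gap is 2π(1.382 − 0.399)(0.3) = 1.85 mm². It is proportional to a. If 0.3 mm were the Week 96 advance at constant speed, the gap at Week 36 would be 1.85 × 36/96 = 0.69 mm². Against a reading error that does not shrink, size explains less of the spread at Week 36, so r is probably lower there.

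**The case against.** The strongest reply is that nothing depends on this analysis. The endpoint is exploratory, has no alpha allocation and no formal test, and describing an outcome that may be zero for many eyes is a legitimate choice. That stands, and it sets the priority.

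Three further points also stand. The change score already uses baseline area by subtracting it; what is missing is covariate adjustment. Imbalance in the presence of atrophy would be visible, because the proportion with atrophy at baseline is itself reported; imbalance in area would not be, unless area by arm is added. And the documents nowhere say that growth depends on starting size, so a gain of zero cannot be excluded. It may also be objected that a linear model suits skewed, mostly zero changes poorly, but the planned interval for a difference in means has the same weakness.

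A reader might infer three stronger things that the documents do not support:

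- That the planned comparison is biased or has inflated error. Step 3 shows 4.97% over randomizations; the result misleads only given an imbalance that actually occurs.
- That adjustment would remove a large, known share of the variance. Simulations of circular growth give reductions from about 10% to 73% at Week 96 and 6% to 48% at Week 36, depending on assumed prevalence, lesion size, border speed, new-lesion rate and reading error. None of these inputs is in the protocol or SAP.
- That this is a planned safety comparison. Atrophy sits under exploratory efficacy and is absent from the safety objective and the ocular events of special interest.

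**Conclusion.** The point holds in limited form: SAP 4.4.3 omits a baseline-area adjustment that the SAP's handling of CPT and CST would lead one to expect, using data the trial already has. The cost of the omission is a CI wider by an amount that depends on an unknown r: nothing at r = 0, under 5% up to r = 0.3, and 20% at r = 0.6. There is also some exposure to chance imbalance in baseline area. These figures assume a linear relation, all 418 patients contributing and simple randomization; missing images or restriction to eyes with atrophy would make the imbalance larger. No primary or key secondary conclusion is affected. It is an optional improvement.

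**What to change.** In SAP 4.4.3, keep the descriptive tables and add an adjusted between-arm difference in change in macular atrophy area, with its 95.03% CI, at Weeks 36, 48 and 96. Use ANCOVA at each visit or the primary MMRM form, with treatment, baseline atrophy area, an indicator for any baseline atrophy, and the BCVA stratum. A square-root transformation of baseline area is optional. State that eyes without atrophy at baseline enter with area zero, and report baseline area by arm.

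SAP version 3 was written after the Primary and Update CSRs were complete, so any adjusted Week 36 and Week 48 results should be labelled post hoc. The Week 96 analysis can still be specified before the final analysis.

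The cost is a few sentences in the SAP and one model per visit. No new data are needed.
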